APPENDIX 6 CONTINUED FROM PREVIOUS PAGE

Other investigations to be performed at UK NAC at the following timepoints:

- PLEASE NOTE – prior to starting each cycle at RHC a 5ml serum sample must be collected and sent to UK NAC
- * Baseline at UK NAC, at UK NAC visit following 3rd cycle of study treatment, at UK NAC visit 6 months after registration or 1 month after the end of study treatment if 6 cycles given and on posted serum samples and on each posted sample sent by RHC as defined in protocol
- ** Baseline visit to UK NAC and at UK NAC visit 6 months after registration or 1 month after the end of study treatment if 6 cycles given. Bone marrow tests will be done at these time points only if clinically indicated.
- *** Baseline at UK NAC, at UK NAC visit following 3rd cycle of study treatment, at UK NAC visit 6 months after start of treatment or 1 month after the end of study treatment if 6 cycles given. At RHC ECHO will be done at end of cycle 2 only. Echocardiogram to be repeated at any cycle if clinically indicated for unexpected worsening of cardiac function.
- **** Baseline at UK NAC, 1st cycle of treatment at day 1, 8 & 15 at RHC, day 1 of every subsequent cycle at RHC, at UK NAC visit following 3rd cycle of study treatment, at RHC at end of treatment, visit, at UK NAC visit 6 months after registration or or 1 month after the end of study treatment if 6 cycles given.
 - Serum Free Light Chains*
 - NT-ProBNP****
 - Echocardiography ***
 - Bone marrow aspirate & trephine plasmacytosis**
 - 24 hour urinary light chain type and quantification**
 - Serum monoclonal protein*

APPENDIX 7: AMYLOID STAGE

The amyloid stage definition will be based on the report published by Dispenzieri et al 2004. The stages will be classified as follows:

Stage I: Both NT-proBNP and cardiac troponin-T normal defined as NT-proBNP ≤ 36 pMol/L and cardiac troponin T ≤ 0.03 ng/ml (or cardiac high sensitivity troponin T ≤ 0.05 μ g/L)

Stage II: Either one of NT-proBNP or cardiac troponin T abnormal defined as: NT-proBNP > 36 pMol/L *or* cardiac troponin T > 0.03 ng/ml (or cardiac high sensitivity troponin T > 0.05 μ g/L)

Stage III: Both NT-proBNP **and** cardiac troponin T abnormal defined as: NT-proBNP > 36 pMol/L **and** cardiac troponin T > 0.03 ng/ml (or cardiac high sensitivity troponin T > 0.05 μ g/L)

1.1 Background

Amyloidosis is a disorder of protein folding in which normally soluble proteins are deposited as abnormal, insoluble fibrils that progressively disrupt tissue structure and impair function. Systemic AL amyloidosis, which is the commonest amyloid type, is a malignant disorder occurring in a small proportion of individuals with monoclonal B cell dyscrasias and AL amyloidosis is a myeloma defining criteria according to the international working group definition of myeloma 2003 (Kyle 2003). AL amyloidosis occurs at an incidence of 3-5 cases per million population and is the cause of death of between 0.5-1 per thousand individuals in the UK. AL fibrils are derived from monoclonal immunoglobulin light chains which are unique in each patient underlying the remarkably heterogeneous clinical picture in this particular form of amyloidosis; virtually any organ or combination of organs other than the brain may be affected. Treatment in AL amyloidosis is aimed at suppression of the underlying B cell dyscrasia using chemotherapy regimens based on those used for multiple myeloma. Without therapy it is inexorably progressive and until recently the median survival was just 6-15 months. Survival for patients who achieve a less than VGPR or refractory patients is even poorer (Palladini, Dispenzieri et al. 2012).

Many studies have demonstrated a link between hematologic responses and improved organ function and survival. Stopping the production of the toxic light chain species can translate into significant benefit for most patients except those with most advanced organ involvement, while stable hematologic disease despite therapy means it is likely that the effects of the toxic light chain species will continue. Consensus criteria for hematologic and cardiac response have been recently developed and validated (Palladini, Dispenzieri et al. 2012). Advanced cardiac and extensive organ involvement limit benefits that can be derived from treatment including eligibility for autologous stem cell transplantation (ASCT) and can shorten survival despite treatment (Merlini, Seldin et al. 2011, Cordes, Dispenzieri et al. 2012). Another treatment limitation is related to the type of organ involvement predisposing patients to the adverse effects of specific drugs. In AL amyloidosis clinical trials, it has been a challenge to distinguish drug-specific side effects from disease-mediated organ dysfunction (Comenzo, Reece et al. 2012)

Carfilzomib (PR-171) is a tetrapeptide ketoepoxide-based inhibitor specific for the chymotrypsin-like active site of the 20S proteasome. Carfilzomib is structurally and mechanistically distinct from the dipeptide boronic acid proteasome inhibitor bortezomib (Velcade®). In addition, when measured against a broad panel of proteases including metallo, aspartyl, and serine proteases, carfilzomib demonstrated less reactivity against non-proteasomal proteases when compared to bortezomib. There is limited data on the use of carfilzomib in AL amyloidosis, we therefore propose a gradual dose escalation study. There is an ongoing study of carfilzomib in AL amyloidosis.

Proteasome inhibitors are associated with highest response rates in AL amyloidosis. Bortezomib has toxicity and limitations in AL amyloidosis. In particular, the high specificity of carfilzomib for proteasome inhibition and its favorable toxicity profile makes it very appealing in AL amyloidosis. For instance, toxicities which commonly complicate Bortezomib use, such as autonomic and peripheral neuropathy, appear uncommon with carfilzomib. Combination of proteasome inhibitors with Immunomodulatory Drug (IMiDs) appears to be synergistic in myeloma and the phase II data using carfilzomib with lenalidomide or thalidomide appears promising. In the UK, we have extensive experience using thalidomide in the treatment of patients with AL amyloidosis. Combining carfilzomib with thalidomide offers an attractive treatment option for patients with relapsed refractory disease due to their non-overlapping toxicity profile. Low dose thalidomide is generally well tolerated by patients with AL amyloidosis but as single agent has limited efficacy. However, in combination with other agents, response rates are high as we have documented by using risk adapted CTD regime. This study is designed to improve the response rates seen with CTD protocol by using carfilzomib in combination with thalidomide and dexamethasone.

1.2 Design

This will be a single arm open label multicentre phase Ib dose escalation study with expansion phases.

Patients will receive treatment with Carfilzomib in escalating dose cohorts along with a fixed dose of Dexamethasone and Thalidomide (KTD). The dose escalation phase of the study will use a 3+3 dose escalation design. Cohorts of 3-6 participants will be treated with KTD as outlined in the Section 8. Carfilzomib doses will be increased between cohorts until the occurrence of dose limiting toxicities (DLTs) define the MTD. The Safety Review Committee will review the safety and ethics of the trial by reviewing interim data after each cohort of treatment during recruitment to the Dose Escalation Cohort. Once the MTD and/or RD has been established a maximum of 20 participants will be recruited for entry into the expansion phase of the study at the RD.

1.3 Aims

The Catalyst (Carfil-thal-Dex in AL treatment) Trial aims to assess the safety and tolerability of KTD (Carfilzomib-thalidomide-dexamethasone) using the phase 1 dose escalating component to define the maximum tolerated dose (MTD) and recommended dose (RD) and the expansion cohort to further assess the safety and tolerability and to gain an understating of efficacy to allow design for further trials.

Primary:

Dose escalation

To define the MTD and RD of Carfilzomib used in combination with Thalidomide and Dexamethasone in patients with relapsed or refractory AL amyloidosis

Dose expansion

To further assess the safety and tolerability of KTD at the RD of Carfilzomib identified in the dose escalation phase

Secondary:

To make a preliminary assessment of the activity of KTD in patients with relapsed refractory AL amyloidosis

1.4 Sample size and expected accrual

In the dose escalation phase of this study, a minimum of 6 (3 at dose level 0 and 3 at dose level -1) and a maximum of 18 (6 at dose level 0 1 and 2) patients will recruited in a 3+3 design with cohorts of between 3 and 6 patients, in order to determine maximum tolerated dose and recommended dose.

At the recommended dose level identified, a further 20 patients will be recruited to further assess safety and toxicities at the RD.

The study will run in 15 UK centres. The study duration is expected to be approximately 42 months – including 6 months of set up, 24 months of recruitment, 6 months of follow-up and 6 months of analysis/write-up.

1.5 Planned analyses

During the Dose Escalation Phase, recruitment will be halted after each group of three patients have completed at least one cycle of KTD, to allow safety data to be assessed. CTRU will produce a summary of DLTs at each dose level, detailed safety listings, and recruitment figures for consideration by the Safety Review Group.

No formal analyses are planned until after the trial is closed to recruitment and the required number of patients has been recruited. Final analysis will be carried out when the required number of patients has been recruited and all patients have been followed up for at least 6 months from registration.

2. Endpoints

2.1 Primary endpoint

Dose-Limiting Toxicities (Dose escalation phase), between the time of receiving the first registered dose of Carfilzomib in cycle 1 and day 1 cycle 2, in order to establish the Maximum Tolerated Dose (MTD) and recommended dose (RD) of Carfilzomib in combination with Thalidomide and Dexamethasone.

Proportion of patients treated who experience any grade 3 or 4 CTCAE toxicity throughout all treatment cycles.

2.2 Secondary endpoints

- Clonal response rate within 3m, at 3m, within 6m and at 6m
- Amyloidotic organ response rate within 3m and 6m
- Time to amyloidotic organ response
- Number of deaths at 6 months
- Number of patients progression free at 6 months
- Maximum response
- Time to maximum response
- Number of patients withdrawing from treatment
- Number of patients experiencing dose delays, and compliance profile of KTD.
- Relative Dose intensity

2.3 Derivation of endpoints

2.3.1 Primary endpoints

Dose limiting toxicities (DLTs) will be collected from the time of receiving the first dose of Carfilzomib in cycle 1 up to the first dose of treatment administered in cycle 2. Only DLTs that are attributed to the registered dose of Carfilzomib will be included when determining the MTD. A DLT will be defined as any of the following events that are determined to be related to trial drug administration:

1. Any non-haematological toxicity \geq Grade 3 according to NCI CTCAE Version 4.03 which fails to return to \leq Grade 1 or baseline after 7 days. Nausea, vomiting, diarrhoea and electrolyte imbalances will be considered DLTs only if they reach \geq Grade 3 severity despite adequate supportive care measures. Similarly, fluid retention or worsening symptoms of heart failure will be considered as DLTs if they are persistent \geq Grade 3 despite increase in oral diuretics or there is an increase in dyspnoea by \geq 2 NYHA grades within 12 hours of administration of Carfilzomib which persists for $>$ 6 hours or needs hospital admission
2. Grade 4 neutropenia lasting $>$ 7 days or Grade 4 neutropenia with sepsis despite adequate supportive measures.
3. Any grade 4 thrombocytopenia which fails to return to Grade 2 within 7 days without platelet support
4. Delay of $>$ 8 days within cycle 1 or delay of commencement of 2nd cycle by more than 14 days, due to significant toxicity or tolerability issue*
5. Any other event which, in the opinion of the Safety Review Committee, is considered to be clinically significant and related to treatment

The MTD is defined as the highest dose level at which no more than 1 patient experiences a DLT, from the time of receiving the first registered dose of Carfilzomib in cycle 1 up to the first dose of treatment administered in cycle 2, i.e. the dose level below that at which 2 or more patients experiences a DLT. If no more than one patient experiences a DLT at the highest dose level then this will be considered as the MTD.

Once the MTD has been established, a minimum of 6 patients will be treated at this dose level in order to establish the RD. The RD is the dose which will be used in the dose expansion phase of the study to evaluate activity.

The proportion of patients treated who experience any grade 3 or 4 CTCAE toxicity will be calculated as number of patients who experience any grade 3 or 4 CTCAE toxicity throughout their treatment cycle.

* This will not be defined as a DLT if the delay is due to one of the other specified DLT criteria.

2.3.2 Secondary endpoints

Clonal response rate (based on paraprotein and FLCs) is defined as the proportion of patients who achieve at least a PR within 3 months, at 3 months, within 6 months and at 6 months after trial registration.

Amyloidotic organ response rate is defined as the proportion of patients who achieve organ response within 3

months and within 6 months of trial registration.

Time to Amyloidotic organ response is defined as the time from the dose allocation to first achieving organ response.

The number of patients experiencing dose delays will be defined as the number of patients experiencing delays in treatment with any of the study treatments.

KTD compliance: Patients will be regarded as compliant to treatment where treatment is received as per protocol until withdrawal from treatment and have no more than 1 dose omission of Carfilzomib, 5 of Thalidomide or 1 of Dexamethasone during each cycle.

Relative Dose intensity will be calculated as the percentage ratio between the received and planned dose intensities, where dose intensity is the cumulative dose divided by the duration of treatment.

3. Analysis Sets

Statistical analysis will be descriptive for all endpoints, and will be summarised overall and by dose cohort. All safety analyses will be based upon the safety analysis set; safety data from patients not included in this analysis set will be listed separately. All efficacy analyses will be based upon the per protocol set. Patients who do meet the criteria to be included in each of analysis sets will have the reasons for emission listed. A sensitivity analysis on the efficacy endpoints may be considered if the total number of patients in each of the analysis sets differs by more than 3 patients.

3.1 Eligibility

Participants considered eligible for the study are those that fulfil all the inclusion and none of the exclusion criteria noted in the protocol. All participants in the analysis population should remain in the trial after registration unless they explicitly withdraw consent. If a participant is found to be ineligible after registration they will be included in the analysis population as appropriate unless written informed consent has not been obtained. If a participant withdraws consent from further trial treatment and / or further collection of data their samples will remain on file.

3.2 Safety analysis set

All patients that receive at least one dose of Carfilzomib and with no protocol deviations with relevant impact on safety will be included in the safety analysis set.

3.3 Per protocol set

The per protocol set will include all patients with at least one post baseline efficacy assessment who receive at least one dose of Carfilzomib and have no protocol deviations with relevant impact on efficacy.

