Statistical summary:	
Sample Size
 
In the dose escalation phase of this study, a minimum of 6 (3 at dose level 0 and 3 at dose level -1) and a maximum of 18 (6 at dose level 0, 1, and 2) patients will be recruited in a 3+3 design with cohorts of between 3 and 6 patients, in order to determine maximum tolerated dose (MTD) and recommended dose (RD). At the recommended dose level identified, a further 20 patients will be recruited to further assess safety and toxicities at the RD.
 
Analysis sets and dose cohorts
 
All patients that receive at least one dose of Carfilzomib will be included in the safety analysis set.
 
The per protocol analysis set will include all patients with at least one post baseline efficacy assessment who receive at least one dose of Carfilzomib and have no protocol deviations with relevant impact on efficacy.
 
Determination of the MTD in the dose escalation phase of the trial will be based on those patients who have received at least one cycle KTD and will be evaluated between the time of receiving the first dose of Carfilzomib in cycle 1 and the first dose of treatment in cycle 2. The safety review committee will review each DLT and attribute the DLT to the loading dose or the registered dose; any DLT attributed to the loading dose will be excluded when determining the MTD. KTD Patients who do not receive one complete cycle due to experiencing a DLT will be included in the analysis; patients who do not receive at least one complete cycle for reasons other than toxicity, without experiencing a DLT, and who miss a dose of Carfilzomib, more than 14 doses of Thalidomide or 2 doses of Dexamethasone in the first cycle, will be replaced. Evaluability will be considered by the safety review committee on an individual basis to account for attributing DLTs and missed doses to the loading or the registered dose. The RD cohort will include all patients who are registered to receive and receive at least one dose of Carfilzomib at the RD. This cohort will include patients from the dose escalation and dose expansion phases of the study. All patients who do not fulfill this criteria will be included in the non-RD cohort.
 
All safety analyses will be based upon the safety analysis set; safety data from patients not included in this analysis set will be listed separately. All Efficacy analyses will be based upon the per protocol set.
 
Primary endpoints and analysis
 
The number of patients experiencing DLTs within the first cycle of KTD will be presented, with descriptive summaries of the specific DLTs observed. Summaries will be presented for each dose level. This data will be presented for patients registered to the dose escalation phase of the study only.

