19.2 General Considerations

Statistical analysis of clinical endpoint data is the responsibility of the CTRU Statistician. A full statistical analysis plan will be written before any analyses are undertaken. The analysis plan will be written in accordance with current CTRU standard operating procedures and will be finalised and agreed by the following people: the trial statistician and supervising statistician, the Chief Investigator, the CTRU Delivery and Scientific Leads and the Senior Trial Manager. Any changes to the finalised analysis plan, and reasons for changes, will be documented.

All patients that receive at least one dose of Carfilzomib and with no protocol deviations with relevant impact on safety will be included in the safety analysis set.

The per protocol set will include all patients with at least one post baseline efficacy assessment who receive at least one dose of Carfilzomib and have no protocol deviations with relevant impact on efficacy.

Determination of the MTD in the dose escalation phase of the trial will be based on those patients who have received at least one cycle KTD and will be evaluated between the time of receiving the first dose of Carfilzomib in cycle 1 and the first dose of treatment in cycle 2. The safety review committee will review each DLT and attribute the DLT to the loading dose or the registered dose; any DLT attributed to the loading dose will be excluded when determining the MTD.

KTD Patients who do not receive one complete cycle due to experiencing a DLT will be included in the analysis; patients who do not receive at least one complete cycle for reasons other than toxicity, without experiencing a DLT, and who miss a dose of Carfilzomib, more than 14 doses Thalidomide or 2 doses of Dexamethasone in the first cycle, will be replaced. Evaluability will be considered by the safety review committee on an individual basis to account for attributing DLTs and missed doses to the loading or the registered dose.

The RD cohort will include all patients who are registered to receive and receive at least one dose of Carfilzomib at the RD. This cohort will include patients from the dose escalation and dose expansion phases of the study. All patients who do not fulfil these criteria will be included in the non-RD cohort.

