Statistical analysis will be descriptive for all endpoints, and will be summarised overall and by dose cohort. All safety analyses will be based upon the safety analysis set; safety data from patients not included in this analysis set will be listed separately. All efficacy analyses will be based upon the per protocol set. Patients who do meet the criteria to be included in each of analysis sets will have the reasons for emission listed. A sensitivity analysis on the efficacy endpoints may be considered if the total number of patients in each of the analysis sets differs by more than 3 patients.

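### Efficacy is planned only in a per-protocol set that drops dosed patients never assessed after baseline; response in all dosed patients should also be committed

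*SAP*

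**What the plan says.** Both documents assign efficacy to one population. Protocol 1.1: "All Efficacy analyses will be based upon the per protocol set". Protocol 19.2 repeats it ("All efficacy analyses will be based upon the per protocol set"), and so does SAP section 3.

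SAP 3.3 defines that population: "The per protocol set will include all patients with at least one post baseline efficacy assessment who receive at least one dose of Carfilzomib". Patients must also have no deviation that bears on efficacy. Protocol 1.1 and 19.2 give the same definition. None of the three names the test or visit that counts.

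Three other provisions bear on the denominator:

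- SAP 5.1 keeps patients with missing values in the denominator, within whichever population applies.
- Protocol 19.2 and SAP section 3 allow a sensitivity analysis of efficacy that "may be considered if the total number of patients in each of the analysis sets differs by more than 3 patients". Its population is not named.
- Reasons for leaving a set are to be listed, but the sentence reads: "Patients who do meet the criteria to be included in each of analysis sets will have the reasons for emission listed".

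The safety set, the natural comparator for that trigger, has two definitions. Protocol 1.1: "All patients that receive at least one dose of Carfilzomib will be included in the safety analysis set". Protocol 19.2 is narrower: "All patients that receive at least one dose of Carfilzomib and with no protocol deviations with relevant impact on safety". SAP 3.2 follows the narrower one ("with no protocol deviations with relevant impact on safety will be included in the safety analysis set").

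**The concern.** A dosed patient who leaves before any qualifying assessment has no response recorded. The plan removes that patient from the denominator and does not count a non-response. Patients who die early or decline further data are the likeliest to be in this position, so the removals are not neutral with respect to outcome.

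Protocol 19.1 makes clonal response the main measure of activity, and Protocol 3.1 says the expansion cohort should inform the design of later trials. The stated rate may therefore be carried forward as a planning assumption. Its denominator would depend on a definition not fixed in advance, with no committed all-dosed figure to set beside it.

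**Working it through.** **1. Which assessment could qualify.** The assessment table in Protocol 11.0 labels the 5 ml serum sample as the one used to judge response. Its footnote and Protocol 11.2 say the same, and a sample is due before each cycle.

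- The cycle 1 sample precedes any carfilzomib, so it is hard to call post-baseline. If it did count, almost nobody would be lost.
- The first on-treatment draw is before cycle 2. This is the most natural reading.
- The table also lists a response assessment at the National Amyloidosis Centre before cycle 4 and at follow-up. If only that counts, the window for loss is longer.

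**2. Who is lost.** Stopping treatment does not by itself remove a patient. Protocol 14.1.1 keeps such patients in follow-up, and Protocol 9.4 and 11.2 provide a visit 6 months after registration. The patients lost are those who die, refuse further data (after which Protocol 14.2 allows only safety data) or miss every later visit before a qualifying assessment. Protocol 21.5 keeps data already collected, so someone who refuses after a qualifying sample stays in.

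**3. Direction.** Let r be responders, N dosed patients and k dosed patients never assessed. The all-dosed rate is r/N and the per-protocol rate is r/(N − k). None of the k can be among the r, so r/(N − k) exceeds r/N when r > 0, and both are zero when r = 0.

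**4. Size.** The plan states no response rate, precision target or early-loss rate, so there is no figure of its own to reproduce. N = 26 comes from at least 6 patients at the recommended dose before expansion (Protocol 8.1.3) plus 20 in expansion (Protocol 19.1). The values of r and k are assumptions.

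| r | r/26 | k = 1 (r/25) | k = 2 (r/24) | k = 3 (r/23) | Rise, points |
|---|---|---|---|---|---|
| 10 | 38.5% | 40.0% | 41.7% | 43.5% | 1.5 to 5.0 |
| 14 | 53.8% | 56.0% | 58.3% | 60.9% | 2.2 to 7.0 |
| 18 | 69.2% | 72.0% | 75.0% | 78.3% | 2.8 to 9.0 |

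The exact (Clopper-Pearson) interval for 14/26 is 33.4% to 73.4% at 95% and 36.2% to 70.8% at 90%.

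**5. Deviation exclusions** can go either way. Removing 2 patients from 14/26 gives 12/24 = 50.0% if both responded, 13/24 = 54.2% if one did and 14/24 = 58.3% if neither did.

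**6. The sensitivity trigger.** Assume 18 + 20 = 38 patients are dosed, and compare the safety and per-protocol totals.

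- With the Protocol 1.1 safety set (38), the difference equals the number excluded from the per-protocol set. Differences of 38 − 37 = 1, 38 − 36 = 2 and 38 − 35 = 3 are not more than 3. Only 38 − 34 = 4 meets the condition.
- With the Protocol 19.2 and SAP 3.2 definition, suppose 2 patients also leave the safety set. Five per-protocol exclusions then give 36 − 33 = 3, which does not meet it. Under Protocol 1.1 the same five give 38 − 33 = 5, which does.

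Even when the condition is met, the analysis is only one that may be considered.

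**7. The missing-data rule.** SAP 5.1 counts missing values as part of the denominator of the appropriate population. For efficacy that is the per-protocol set, so the rule does not bring back a patient already outside it.

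**The case against.** The strongest reply is that the practical effect is slight. Efficacy is secondary and descriptive, with no test and no decision rule. The illustrated rise of 2.2 to 7.0 points sits inside a 95% interval 40 points wide (73.4 − 33.4). On the cycle 2 reading, a patient is lost only with no sample from cycle 2 onward and no later centre visit. The 6 escalation patients who must complete cycle 1 before expansion opens are unlikely to be among them. Eligibility requires a life expectancy of at least 6 months and excludes the most advanced cardiac disease, which makes very early loss less likely. SAP 3.1 keeps patients found ineligible after registration in the analysis as appropriate. If reasons for omission are listed as presumably intended, a reader could largely rebuild the all-dosed rate. All of this stands, and it limits the point to a minor one.

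It does not remove the gap. No provision commits to an all-dosed efficacy summary, and the direction of the effect for unassessed patients is fixed.

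Three stronger readings are tempting but not supported:

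- A reader might infer that the efficacy assessment cannot be identified at all. The schedule does identify a response test; what is missing is a link from the set definition to it.
- A reader might infer that everyone who stops early is dropped. The follow-up provisions contradict that.
- A reader might infer that no population is named for progression-free status at 6 months. The rule covering all efficacy analyses reaches it; only the count of deaths is arguably left open.

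**Conclusion.** The point holds as a minor one. The plan's only committed efficacy population excludes dosed patients with no qualifying post-baseline assessment. Neither the missing-data rule nor the optional sensitivity analysis restores them. For these patients the effect is one-sided: the response rate rises, or stays at zero.

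The illustrated size is 56.0% to 60.9% instead of 53.8% for 1 to 3 exclusions. This assumes 26 dosed patients at the recommended dose, 14 responders and no other exclusions. With 10 to 18 responders the rise runs from 1.5 to 9.0 points. Nothing in the documents suggests how many patients would be lost, and on the cycle 2 reading it is probably few. A claim of material bias would go beyond the text. What is certain is the gap in the definition and the absence of a committed all-dosed summary.

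**What to change.** In Protocol 1.1, Protocol 19.2 and SAP section 3:

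- Commit to reporting clonal and organ response in every patient given any carfilzomib, by registered dose level, with no assessment counted as non-response.
- Use the same all-dosed set for deaths and progression-free status at 6 months.
- Report the per-protocol result beside it, with the qualifying assessment defined, for example as the first serum response sample after the start of treatment.
- Delete the condition on a difference of more than 3 patients, which then has no purpose.

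Three drafting corrections are separate from the main point but belong in the same revision:

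- Reconcile the safety set of Protocol 1.1 with that of Protocol 19.2 and SAP 3.2.
- Reconcile SAP 3.5 with SAP 5.1. An expansion patient given only the day 1 loading dose is in the non-RD cohort under SAP 3.5 but fits neither population in SAP 5.1.
- Correct the sentence on reasons for omission in Protocol 19.2 and SAP section 3, so that it covers patients who do not meet the criteria.

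The cost is wording in both documents, one extra table and a possibly slightly lower stated response rate. No new data are needed.
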